Note that in NZ, TdaP has been recommended in pregnant women between 20 and 36 weeks gestation since 2011 but had to be privately purchased. In October 2012, the MoH recommended and began fully funding TdaP nationally for pregnant women who were between 28 and 38 weeks gestation. There will be some variation, mainly prior to this date as some women will have received it both earlier and later than this in a range of regionally funded programmes. We are able to identify these exposures in the regionally funded programmes. We will not be able to identify private purchase. We know from anecdotal evidence that the number of women purchasing prior to funded programmes was very low but we cannot accurately quantify. GSK NZ have followed this up and confirm very few doses.

While TdaP was available via fee-for-service as early as 20 weeks gestation, a selection of DHBs began funding TdaP in pregnant women in 2012. Each DHB decided the gestation period required to receive funded TdaP. For example, Counties Manukau DHB-funded TdaP for women after 20 weeks gestation while Canterbury DHB funded TdaP for women between 30 and 36 weeks gestation. Again, these exposures can be identified.

Study participants

Hospitalisation data for the study period will be obtained from the National Minimum Dataset. Health outcomes in the study population that required contact with a hospital will be described for mothers by health outcome type and incidence per maternal age, ethnicity, deprivation, vaccination exposure and time interval from vaccination. For infants the health outcomes in the study population that required contact with a hospital will be described by infant ethnicity, age, deprivation, maternal age, ethnicity and deprivation and whether or not vaccination was given during pregnancy. The data for infants included in Study One will include the first year of life.

Vaccination status will be determined through the claims information submitted to the DHB and matched to the hospitalisation data. Notifications for pertussis will be determined from Environmental Science and Research (ESR) who provide disease surveillance to the government. ESR, under contract to the MoH, undertakes laboratory based surveillance of notifiable diseases and outbreak surveillance. Hospitalisations will be determined through the National Minimum Dataset. Hospitalisations and notifications will be matched to vaccine status using the National Health Index Number (NHI).

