Vaccinee data verified as non-duplicated, then NHI number, name and phone number will be replaced by a sequential number (These are the only variables that contain personal identifiable information and will also be used to ensure there is no duplication of survey and extraction of maternal and pregnancy data at the end of the study).

Data set validation

Data set will be double entered for validation

Any corrections will be reviewed by a third party

Data confidentiality

No names or NHI numbers will be published

Visibility of the National Health Index number (NHI) of the participant's records will be password protected and restricted to the key investigators before being removed at the end of the study.

Access to complete data sets will be limited to the investigators and data analysts.

Data storage

The datasets will be stored in a password-protected file within The University of Auckland and the physical files will be held in a locked filing cabinet by the Principal Investigator/s [name] who will store it for 10 years in accordance with the NZ ethical guidelines.

Study duration

	Intensive study	Population datalink study
Month one	First participants enrolled in intensive study	
Month six	Last participants enrolled in intensive study (this potentially may be extended depending on enrolment)	Preparation for population data collection. Obtain ethical approval
Month 12	Interim report due	Receive 2009-2013 data, commence data cleansing and data matching
Month 18	Last of the 1 year follow up data will be collected	Commence analysis
Month 20	Final study report due	
Month 22	Submission of publication	
Month 24		Final report
Month 28		Submission of publication

Statistical analysis and sample size justification

Study One (N=~325,000)

Sample size:

Over the five-year period of this study there will be approximately 325,000 births. The percentage vaccinated will increase over the time period as the funded vaccine is promoted over the epidemic but on average approximately 30% of mothers would be expected to have received vaccination during pregnancy.

Analysis:

Logistic regression will be used to estimate odds ratios for the risk for (specific) adverse events for both mothers and infants in vaccine exposed and unexposed groups. Age, ethnicity and socioeconomic deprivation and season for hospital admission will be included as additional explanatory variables.

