As specific diagnoses are not necessarily independent events each person will only be counted once for each hospitalisation, the primary diagnosis and repeat admissions for the same episode will be removed, including transfers from one hospital to another.

For diagnosis where individuals may have multiple admissions for different occurrences and the outcome is a count, Poisson regression will be used with testing and adjustment for overdispersion where required.

The temporal relationship between onset of events and vaccination will be presented including distribution where appropriate,

Serious adverse events will be reported as detailed clinical cases.

To analyse the effect of Tdap on still births we will perform a survival analysis. The time dependent explanatory variable of vaccination status and 'failure' of still birth and censored at birth, also including demographics as explanatory variables. The independent explanatory variable will be Tdap vaccination status of the mother (time dependent). Time will commence at the beginning of the inclusion time for an individual— 28(20) weeks gestation. Women will be censored at time of live birth or at the end of the study period, 31 December 2013, whichever occurs first.

Study Two (N=~300)

Estimated number of women receiving pertussis vaccine during pregnancy for study period, potential study population

The birth cohort in NZ is approximately 65,000 per annum. Tdap is funded for pregnant women, but it is difficult to estimate how many women will take up the vaccine. In one DHB with a birth cohort of 6,000 who were first to offer pertussis vaccine free to pregnant women, 220 claims for the Tdap vaccine had been lodged in six weeks and 1,164 over eight months. At the 10th June 2012, out of 255 claims processed at that time 22 (9%) of women had not consented to follow up. The number of women able to be recruited to the Canterbury study is limited by available nurse time.

Based on the experience in Canterbury assuming sufficient workforce capacity the potential number of women available for follow up over a one-year period is:

National birth cohort 65,000

Uptake of pertussis vaccine in pregnancy 10–40%

Potential annual vaccinated cohort 6,500–26,000

Likely to consent (90%) 5,850–23,400

Eligible to participate (87%) 5,090–22,620

- Participation by general practices (success in obtaining informed consent to follow up) estimate 30–90% (likely to be higher rather than lower)

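### Study One's stated covariate list omits District Health Board, although early Tdap funding and eligibility were set by each board

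*Protocol*

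**What the plan says.** The Study One analysis is set out in the Protocol under Statistical analysis and sample size justification. The main model is fixed there: "Logistic regression will be used to estimate odds ratios for the risk for (specific) adverse events for both mothers and infants", comparing vaccine-exposed with unexposed groups. The covariates follow: "Age, ethnicity and socioeconomic deprivation and season for hospital admission will be included as additional explanatory variables". Count outcomes get Poisson regression with an allowance for overdispersion. The stillbirth survival model adds demographics to time-dependent vaccination status. None of the three models names a DHB or region term.

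The Study population text for Study One describes how women came to be exposed. Before national funding, "a selection of DHBs began funding TdaP in pregnant women in 2012", and "Each DHB decided the gestation period required to receive funded TdaP". Its two examples are one board funding after 20 weeks and another funding at 30 to 36 weeks. The regional phase then gave way to a single scheme: "In October 2012, the MoH recommended and began fully funding TdaP nationally for pregnant women who were between 28 and 38 weeks gestation".

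**The concern.** On the protocol's own account, during part of 2012 a woman's DHB helped decide whether and when she could receive funded Tdap. A variable that determines exposure becomes a confounder if it is also related to outcome. The stated covariates contain nothing that stands for it.

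The documents link DHB to an outcome in one place. Appendix 8 describes the Canterbury board funding Tdap during a regional outbreak with laboratory-confirmed pertussis at 10 times baseline, and pertussis is among the Study One infant outcomes. Pertussis was also rising nationally, and the size of any regional contrast is not given.

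Study One is the component that compares vaccinated with unvaccinated pregnancies across the whole population, so it carries most of the weight of the clinical hypothesis that event rates are similar. An uncontrolled DHB effect could produce either a false safety signal or false reassurance.

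**Working it through.** **Inputs from the Protocol.** "Over the five-year period of this study there will be approximately 325,000 births" (Study One, Sample size). "The birth cohort in NZ is approximately 65,000 per annum" (Study Two sample size text). One early board had 6,000 births a year and 1,164 claims over eight months. National uptake is put at 10–40%.

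**Not in the documents, so assumed.** The number of DHBs (11, from 65,000 / 6,000 ≈ 10.8, or 20), the ICC, the spread of uptake between DHBs, and outcome risk.

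**1. The plan's own figure.** 65,000 × 5 = 325,000 births, which reproduces. Study One states no alpha, power or detectable odds ratio, so nothing else can be reproduced.

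**2. Direction and size of bias.** Take two groups of DHBs and a true odds ratio of 1. The first group holds a share s of births, with uptake u1 and risk p1. The rest have uptake u0 and risk p0. Then

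- risk in exposed = [s·u1·p1 + (1−s)·u0·p0] / [s·u1 + (1−s)·u0]
- risk in unexposed = [s(1−u1)·p1 + (1−s)(1−u0)·p0] / [s(1−u1) + (1−s)(1−u0)]

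With s = 0.3, u1 = 30%, u0 = 10%, p0 = 5% and p1 = 6% (1.2 times p0):

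- exposed: (0.0054 + 0.0035) / 0.16 = 0.0556
- unexposed: (0.0126 + 0.0315) / 0.84 = 0.0525
- apparent odds ratio: 1.06

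Varying s from 9% to 30%, with p0 = 5%:

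| Uptake, first group vs rest | p1 = 0.8 × p0 | p1 = 1.2 × p0 |
|---|---|---|
| 30% vs 30% | 1.00 | 1.00 |
| 30% vs 20% | 0.97–0.99 | 1.01–1.02 |
| 30% vs 10% | 0.93–0.97 | 1.03–1.06 |
| 29% vs 0.1% | 0.81–0.83 | 1.15–1.19 |

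The last row mimics the period before national funding. Its 29% is 1,164 / (6,000 × 8/12). There is no bias when uptake is equal, and it can run either way otherwise.

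**3. Standard errors.** When exposure varies within clusters, the variance inflation is about 1 + (m−1) × ICC of outcome × ICC of exposure. With 20 DHBs, m = 325,000 / 20 = 16,250.

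- Exposure ICC 0: inflation 1.00, so no effect.
- Outcome ICC 0.001, exposure ICC 0.01: 1 + 16,249 × 0.00001 = 1.16, so the true standard error is 1.08 times the model's.
- Outcome ICC 0.005, exposure ICC 0.01: 1 + 16,249 × 0.00005 = 1.81, so 1.35 times. A nominal 5% test then has size P(|Z| > 1.96/1.35) ≈ 15%.

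**4. Simulation under no vaccine effect.** Outcome risk was 7%, with 11 or 20 DHBs and 300 replicates per cell. Exposure was zero in 2009–2011, partial in 2012 with more in early-funding DHBs, and full in 2013. DHB risks had variance ICC × p(1−p). At ICC 0.005 the between-DHB SD is √(0.005 × 0.07 × 0.93) = 1.8 percentage points. At ICC 0.001 it is 0.8 points.

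| DHB uptake | ICC | False positives, no DHB term |
|---|---|---|
| equal, or 20–30% | 0.001 | 3–8% |
| equal, or 20–30% | 0.005 | 4–13% |
| 10–40% | 0.005 | 18–22% |

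With DHB and year in the model the rate was about 2–8%. The simulation error around 5% is √(0.05 × 0.95 / 300) = 1.3 points, so that range is compatible with nominal. With the 10–40% spread at ICC 0.005, year without DHB left the rate at 17–19%. Person-level covariates were not simulated, so the ICC should be read as what remains after the listed adjustments.

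**The case against.** The strongest reply is that board-set access was brief. From October 2012 one national window applied. At 10–40% uptake, the 15 months to December 2013 give 65,000 × 15/12 × (0.10 to 0.40) = 8,125 to 32,500 vaccinated women, against 1,164 claims in the one early board quantified. Most exposure therefore probably arose under the national scheme. This stands and limits the size. It does not remove the regional phase, and the documents are silent on how uptake varied between DHBs afterwards.

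A reader might also infer three stronger things that the documents do not support:

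- **That births are treated as independent.** The protocol never says so. It handles repeated diagnoses and overdispersed counts, and the variance method may be set in an analysis plan that is not shown.
- **That regional coding and admission practice distorts the outcomes.** No section reports such differences. The sources are national collections, preterm status comes from a gestational-age field, and stillbirths are recorded in the Mortality Collection.
- **That DHB uptake ranges over 10–40%.** That range expresses uncertainty about one national figure. Read as a between-DHB spread, it produces most of the excess false positives.

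It is also fair that the covariate sentence does not exclude other terms, and that the vaccinated-versus-unvaccinated comparisons are secondary objectives. Neither point explains why a documented determinant of exposure is missing from the covariates that the protocol chose to name.

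**Conclusion.** The concern holds in a conditional and modest form. The stated covariates leave out a variable that the protocol itself ties to exposure. Harm requires DHBs to differ in both uptake and outcome after adjustment for age, ethnicity, deprivation and season. The first is documented for the regional phase only; for the second there is no figure. Under the narrower uptake spreads, the false-positive rate is near nominal at ICC 0.001 and about 4–13% at ICC 0.005. It reaches 18–22% only if DHB uptake spans 10–40%. The ICC, the number of DHBs and the uptake spread are all assumptions. The documents do not support saying that regional differences will be counted as vaccine effects, or that the standard errors are known to be too small.

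**What to change.** In the Study One Analysis text, add DHB of domicile as a fixed effect or stratum, together with calendar year, to the logistic and Poisson models. Add DHB as a stratum in the stillbirth survival model. Keep the model without DHB as a sensitivity analysis, so that a reader can see how far region moves each odds ratio. Year belongs beside DHB because funded exposure begins only in 2012; it does not replace DHB.

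The cost is one or two sentences and two categorical covariates. At 7% risk, the DHB term raised the mean standard error by under 1%. Year will cost somewhat more, because the 2009–2011 births, with almost no funded exposure, then contribute little to the comparison. No new data collection is needed if the national extracts carry a DHB field for vaccinated and unvaccinated women alike. The documents do not list the fields, so this should be confirmed before the data request is final.

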Intensive safety monitoring (Study Three) *Canterbury District Health Board (DHB), [name] (PI)*

To describe adverse events in women who were administered Tdap under the DHB programme between 30–36 weeks of gestation

To describe outcomes of babies whose mothers were vaccinated with Tdap in the Canterbury region during week 30 to 36 of pregnancy (including birth history, weight and head circumference and any congenital abnormalities)

Clinical hypothesis

The rates and patterns of adverse events following administration of Tdap during pregnancy (including the rates and patterns of any adverse pregnancy outcome, and the outcomes in infants up to one year of age), are similar to those where no vaccination during pregnancy occurred.

Background

New Zealand (NZ) is currently experiencing a significant increase in pertussis. The number of notified cases has risen dramatically from July 2011 and remained high throughout 2012. Increases in pertussis notifications have been seen previously and occur over a four- to five-year cycle in NZ. The underlying reasons for such a cycle are unknown.

Notification data and associated rates by age indicate that the under-one-year-olds are the most vulnerable with a cumulative notification rate in 2012 of 606 per 100,000 or 378 cases, 167 being hospitalised. This is the highest cumulative notification rate of any age group in 2012. There were 40 notifications of infants under six weeks old, 36 of which were hospitalised.

In 2012 (up to 23 November) 287 hospitalisations were reported. Of these, 167 (58.2%) were infants under one year old. Two deaths were reported, one in a three-year-old unimmunised child with underlying health conditions, and one in an infant aged less than six weeks with a history of preterm birth. All infants hospitalised with pertussis infection younger than six weeks of age have not received their first pertussis immunisation. Data in NZ shows about 20% of infant cases are infected by their mothers.¹

The most recent data for the two surveillance weeks (24 November–7 December 2012) showed 248 new cases of pertussis (113 and 135 cases, respectively) notified, including 111 confirmed cases, 92 probable cases, 14 suspect cases, and 31 cases still under investigation. Twenty-nine (11.7%) of the notified cases were aged less than one year. Fourteen cases were hospitalised.

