The large retrospective component to this study adds significant power to the overall study: It is a cost effective method of data collection and enables more effective assessment of seasonality. It will also provide data on a range of pregnancy and birth outcomes which are not readily available from a prospective study design (e.g., Apgar scores).

⁵ New Zealand Ministry of Health. Current advice on the public health management of pertussis. Wellington: MoH; 5 April 2012. Available at http://www.nzdoctor.co.nz/media/1682109/pertussis_letter_moh_5_apr_2012.pdf

⁶ New Zealand Ministry of Health. Chapter 15: Influenza. In Immunisation Handbook 2011. Wellington: MoH; 2011. Available at

http://www.google.co.nz/url?sa=t&rct=j&q=ministry%20health%20influenza%20vaccine%20pregnant%20women%20funded%20&source=web&cd=7&ved=0CGYQFjAG&url=http%3A%2F%2Fwww.health.govt.nz%2Fsystem%2Ffiles%2Fdocuments%2Fpublications%2F15influenza.pdf&ei=8SiWT8iDH4_m8QQgnNGMCG&usq=AFQjCNFUuAYDXQKxJFmqXKd4PBfzm1i2A

⁷ Canterbury District Health Board. Media release from Canterbury DHB: Free whooping cough vaccine extended to pregnant women. Christchurch: CDHB; April 19, 2012.

⁸ Study Three is largely funded by Canterbury DHB, but is being conducted as part on the three-component study covered in this protocol. Study Three runs as per Study Two, except the former study will follow women and their infants for a period of one year after the birth of the infant while the follow up for the latter study is to four weeks post vaccination.

Study design

Study One: Retrospective analysis of safety outcomes for pregnant women vaccinated with TdaP vaccine and their infants.

Study population

All women delivering in NZ for the study period 2009–2013 and their infants will form the overall study population. Study One will identify all pregnancies and all exposures (except the very few who privately purchased the vaccine).

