Rates and patterns of adverse events in women who were administered Tdap during pregnancy

Multiple pregnancies

While the number of visits during pregnancy could have an impact on the pregnancy outcome within the study population in Study Two and Three (but not in Study One). The frequency of prenatal care is a potential confounder as it may be associated both with women receiving Tdap or not, and with birth outcomes. There is no way to capture the number of prenatal visits women have from nationally available data. However, the National Maternity Collection does “contain data on primary maternity services provided under Section 88 of the NZ Public Health and Disability Act 2000. This information is sourced from lead maternity carer claims for payment.” This information might be useable as a proxy to indicate frequency of prenatal care.

Study Three: Intensive monitoring study of pregnant women administered Tdap during pregnancy and their infants

Study Three involves extending and supporting the intensive monitoring study currently being conducted in the Canterbury DHB by [name] (Principal Investigator). Briefly this study runs as per Study Two except the women and their infants are followed up intensively for a period of one year after the birth of the infant. The data collected for the period of one month post vaccination in Study Three will be able to be pooled for the overlapping subset of participants also in Study Two.

Study Three includes women receiving the vaccine under the DHB programme at 30–36 weeks in the Canterbury region.

Figure 1. Study population and outcomes

[figure not shown]
[figure not shown]

Figure 2. Monitoring of pregnant women receiving pertussis during pregnancy

Canterbury DHB continues intensive follow up for birth outcomes and infant outcomes for one year for a sample of 300 women and their infants. Infant follow up at three to seven months and 12 months of age in this DHB as per Canterbury protocol (Study Three) (Appendix 8).

Study procedures

Study One (utilising whole population data-linking)

Data sets for hospitalisations, pertussis notifications, infant vaccination and maternal Tdap vaccination will be obtained for the period 1 January 2009 to year ending 2013 from the following national databases:

- National Minimum Dataset for hospitalisation data
- The National Immunisation Register for infant immunisation data
- Notification data from the ESR
- Pregnancy Immunisation records from the HealthPAC claims database

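### Study One adjusts for season of hospital admission, which has no value for people not admitted, and names no calendar-time term although identifiable Tdap exposure starts only in 2012, mid-epidemic

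*Protocol*

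**What the plan says.** The protocol's statistical section for Study One states: "Logistic regression will be used to estimate odds ratios for the risk for (specific) adverse events for both mothers and infants", contrasting vaccine-exposed with unexposed. The adjustment set follows: "Age, ethnicity and socioeconomic deprivation and season for hospital admission will be included as additional explanatory variables". The same section plans Poisson regression for repeated admissions, with no covariates named, and a survival analysis of stillbirth with time-dependent vaccination status plus demographics. None of the three names year, calendar period, epidemic period or DHB.

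The population is everyone, admitted or not: "All women delivering in NZ for the study period 2009–2013 and their infants will form the overall study population". On size: "Over the five-year period of this study there will be approximately 325,000 births".

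On exposure, the Study One population section says: "In October 2012, the MoH recommended and began fully funding TdaP nationally for pregnant women". It adds that some DHBs funded the vaccine earlier in 2012, that these exposures can be identified, and that earlier private purchase cannot be identified but is thought very rare. Canterbury's announcement is dated 19 April 2012 (footnote to the Background). On the epidemic, the Background says: "The number of notified cases has risen dramatically from July 2011 and remained high throughout 2012". It also says that national funding was for the duration of the epidemic.

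**The concern.** There are two separate faults.

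First, a covariate must have a value for events and non-events alike. If the season is that of the outcome admission, every event has one and no non-event does. The term then cannot be estimated, or the fit is confined to admitted people, which is selection on something vaccination may be associated with.

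Second, season is not calendar time. A winter birth in 2009 and one in 2013 carry the same season value, yet the first could not have had funded Tdap. Any outcome whose frequency changed over the five years, through the epidemic or otherwise, then has part of that change attributed to the vaccine. The clinical hypothesis is that event rates are similar with and without vaccination, so an artefact in either direction can create or hide a signal.

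**Working it through.** **Inputs from the protocol.** Annual births: "The birth cohort in NZ is approximately 65,000 per annum". Uptake once funded: 10–40% (Study Two sample size). National funding: October 2012. Epidemic rise: July 2011. Deliveries outside hospital: about 2% (Study One, Outcomes). **Assumed:** the size and end of the epidemic, and trends in other outcomes.

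**1. The plan's figure.** 5 × 65,000 = 325,000; it reproduces.

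**2. Where exposure lies.** October 2012 to December 2013 is 15 of 60 months: 65,000 × 15/12 = 81,250 births, 25% of the cohort. I apply 30% as uptake in that window (within 10–40%), not as a five-year average; a 30% average would be 97,500 exposed, or 120% of those births. Then:
- exposed: 0.30 × 81,250 = 24,375
- unexposed in the window: 56,875
- unexposed before it: 243,750
- share of the unexposed delivering before national funding: 243,750 / 300,625 = 81%

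Earlier regional exposure: Canterbury's 1,164 claims in eight months is 145.5 a month, so about 786 from 19 April to the end of September 2012 (5.4 months). If one to five DHBs ran at that rate (assumption), 67–98% of identifiable exposure falls in the last 15 months.

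**3. Season term.** If the model is restricted to admitted people and vaccination is associated with other admissions by a ratio r, a true odds ratio of 1 becomes 1/r: 1.25 for r = 0.8 and 0.83 for r = 1.2 (r is assumed).

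**4. Pertussis, no vaccine effect.** Let incidence be 1 before July 2011 (30 months) and k afterwards. Unexposed weight is 1 for the first 45 months and 0.7 for the last 15, total 55.5.

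*Epidemic through 2013:* RR = k / [(30 + 15k + 10.5k)/55.5].

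*Baseline again in 2013:* exposed mean = (3k + 12)/15; unexposed mean = (30 + 15k + 2.1k + 8.4)/55.5.

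| k | through 2013 | baseline in 2013 |
|---|---|---|
| 3 | 1.56 | 0.87 |
| 5 | 1.76 | 0.81 |
| 10 | 1.95 | 0.74 |

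A vaccine that truly halved the risk would show half of each value: 0.78, 0.88, 0.97 in the first case and 0.43, 0.40, 0.37 in the second.

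This assigns risk by birth month. Giving infants born July 2010 to June 2011 the average rate (1 + k)/2, because part of their first year met the epidemic, lowers the first column to 1.41, 1.53, 1.64.

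**5. Other outcomes.** Expected-count logistic regressions were fitted with a true odds ratio of 1, 5% baseline risk, 2% uptake from April to September 2012, then 10% or 40% uptake (the trends, the baseline risk and the 2% are assumptions).

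| Change in outcome | OR, season only | OR, season and year |
|---|---|---|
| +2% a year | 1.04 | 1.00 |
| +5% a year | 1.10–1.11 | 1.00 |
| −5% a year | 0.90–0.91 | 1.00 |
| ×1.5 from July 2011 | 1.21–1.24 | 0.99 |
| ×2 from July 2011 | 1.37–1.41 | 0.98–0.99 |

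For +5% a year the 95% interval is 1.00–1.20 at 10% uptake and 1.06–1.16 at 40%. A mid-year step leaves a small residue after adjusting for year, which favours quarter.

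**The case against.** **Mothers mostly have an admission.** With about 2% delivering outside hospital, a delivery-admission season exists for nearly all mothers and for outcomes of the birth stay. This stands. A reader might infer that the model cannot be fitted at all; the documents do not support that. The gap is in later infant admissions and maternal admissions other than delivery, and the protocol does not say which admission is meant.

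**Exposure is not purely a matter of date.** A reader might infer that it is confined to the last 15 months and that everyone earlier is unexposed by date. Regional programmes began earlier in 2012 and are identifiable, and about 19% of the unexposed are contemporaneous (56,875 / 300,625). The comparison is therefore mixed rather than purely one of years, but period still dominates the unexposed group.

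**The bias has no fixed sign.** A reader might infer that it is upward. High notifications are documented only through 2012, and the Canterbury protocol (Appendix 8) says earlier outbreaks lasted around 18 months, which from July 2011 ends about December 2012. The tenfold figure there is regional and laboratory-confirmed. No coding or admission trend is documented. This stands, and is why both scenarios are shown.

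**Prenatal care.** The protocol says "The frequency of prenatal care is a potential confounder", so its absence might look like a further error. The same paragraph says visit counts cannot be captured from national data and that the claims proxy is only possibly usable. Leaving it out is explained.

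**The SAP may say more.** The covariate list is not declared exhaustive, the SAP is not shown, and Study One's lead objective is background rates, with exposure comparisons secondary. That lowers the urgency. It does not remove a named term that is undefined for part of the cohort, or an adjustment set that leaves period confounding if followed.

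**Conclusion.** The point holds in limited form. The season term is undefined for cohort members without a relevant admission, chiefly for infant first-year and non-delivery maternal outcomes. The stated Study One models leave the vaccine contrast confounded by calendar period, because identifiable exposure starts in 2012, mostly after October, while the epidemic began in July 2011.

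The existence of the confounding follows from the protocol's own dates; its size and direction do not. Under no vaccine effect the crude pertussis risk ratio could lie anywhere from 0.74 to 1.95 across the two epidemic courses, given 30% uptake from October 2012 and k of 3 to 10. For another outcome, an assumed change of 5% a year moves a null odds ratio to about 1.10 or 0.90.

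**What to change.** In the Study One analysis text:

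- Replace season of hospital admission with season or month of birth (infants) or delivery (mothers), which is defined for everyone in the delivering cohort. Season at reaching 28 weeks is not a suitable substitute, because pregnancies that end earlier have no value.
- Add calendar period (quarter, or at least year, of birth or delivery) and DHB to the logistic and Poisson models. Add calendar period to the stillbirth model as well.
- Add a sensitivity analysis restricted to pregnancies with access to funded Tdap by place and date.
- Treat the maternity-claims proxy for prenatal care as optional, to be explored only if the data prove usable.

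Birth and delivery dates should be available from data sets already being requested, so this is a wording change. The statistical cost is that information then comes mainly from contemporaneous births: √[(1/24,375 + 1/56,875) / (1/24,375 + 1/300,625)] = 1.15, so intervals on the log odds ratio are about 15% wider at 30% uptake.
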